13.2. Impact of COMT (Val-Met) Status

Blood samples will be collected for analysis of catechol-O-methyltransferase (COMT) genotype. Sequencing was performed to detect the c.472G>A, p.Val158Met variant (Chr22:19951271) known familial variant ONLY. There will be one of three following results on the report,

- The variant of interest was NOT detected, corresponding to Val/Val
- The variant of interest was detected; heterozygous, corresponding to Met/Val
- The variant of interest was detected; homozygous, corresponding to Met/Met

The impact of COMT status on safety will be investigated by analysis of TEAEs, presented by primary SOC and PT, showing number and percentage of patients with at least 1 TEAE by COMT status (Met/Met vs Met/Val vs Val/Val) on the FAS.

To evaluate the impact of COMT status on pharmacodynamic, subgroup analyses will be conducted on the following pharmacodynamic endpoints based on the mITT set across the three COMT groups (Met/Met vs Met/Val vs Val/Val):

- NPI-C apathy domain score
- NPI apathy domain score
- DAIR score
- AES-C score

The subgroup analysis will be performed by subgroup rather than including an interaction term.

14. SUBGROUP ANALYSES

Subgroup analyses of the key pharmacodynamic endpoints, NPI-C apathy score and NPI apathy score will be made based on the mITT set to assess consistency of the intervention effect across the following subgroups:

- Age group (<75, ≥75)
- Sex: female vs. male
- Baseline NPI-C apathy score: ≤baseline median vs. >baseline median (median of the mITT set regardless treatment group)
- Use of concomitant SSRI/SNRI : yes vs. no

Provided that the sample sizes in the subgroups allow, the MMRM analysis method described in [Section 11](#) will be applied to the subgroup analysis. The subgroup analysis will be performed by subgroup rather than including an interaction term. If the number of subjects within a subgroup is too small (less than 9 subgroup overall or less than 1 in any treatment group), only descriptive statistics will be used for the subgroup analysis.

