4. GENERAL STATISTICAL CONSIDERATIONS

4.1. Sample Size Considerations

While formal hypothesis testing is not the key objective of this trial, the original planned sample size of approximately 75 subjects randomized in a 1:1:1 manner between the placebo and 2 CVL-871 arms should allow the trial to have approximately 80% probability to detect an effect size (treatment difference/population standard deviation [SD]) of 0.678 in change from Baseline on the Neuropsychiatric Inventory (NPI) apathy domain score at Week 12 between an active dose group and placebo, at a 2-sided alpha = 0.2 level (ie, an 80% confidence interval [CI] excluding zero). As a reference, in the ADMET 1 trial (6 weeks of treatment with methylphenidate for apathy in Alzheimer's disease), an effect size 0.5625 (mean difference of 1.8 and SD of 3.2) on the change from baseline in the NPI apathy domain score was observed (Rosenberg et al, 2013). A discontinuation rate of 20% was taken into consideration in the sample size calculation.

At the time of protocol amendment Version 4.0, an assessment of the detectable treatment effect with a sample size of 60 subjects (randomized 1:1:1 to the 3 treatment groups) concluded that an effect size of 0.761 can be detected with 80% power at a 2-sided alpha level of 0.2.

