11. PHARMACODYNAMICS

The planned timepoints for pharmacodynamic assessments are shown in the Schedule of Assessments (Table 4) which will be completed before the safety assessments and by the same identified caregiver.

All pharmacodynamic endpoints will be analyzed through descriptive statistical methods based on the mITT population. Pharmacodynamic endpoints with repeated post-baseline assessments will also be analyzed, using the mITT population, through statistical inference by using a mixed-model repeated measures (MMRM) analysis, including baseline score (if applicable), treatment, concomitant SSRI/SNRI use, visit (only measured at Visit 5 and 6), and the interaction between treatment group and visit as fixed factors in the model. Subject will be included as a random effect in the model.

An unstructured correlation matrix will be used to model the within-patient errors covariances. The Kenward-Roger approximation will be used to estimate the denominator of degrees of freedom. The least square (LS) mean of each treatment group, difference in the LS mean between the treatment groups, and the corresponding 80% and 95% CI of the differences and p-values will be provided.

If the MMRM model fails to achieve convergence due to complexity of model specification, different covariance structures will be used according to the following order till convergence is achieved:

1. Unstructured correlation (UN)
2. Heterogeneous Toeplitz (TOEPH)
3. Homogeneous Toeplitz (TOEP)
4. First-Order Autoregressive [AR(1)]
5. Compound Symmetry (CS)

The key research questions for the pharmacodynamic endpoints (ie, effect of CVL-871 treatment groups versus placebo) will be primarily addressed with a hypothetical strategy. As such, the missing values will be considered as missing at random (an MMRM analysis assumption).

The primary analysis for all PD endpoints will be performed as described above. However, if the number of subjects with evaluable baseline and post-baseline assessments for a specific PD endpoint is smaller than 15 (all treatment groups combined) or smaller than 2 in any treatment group, only descriptive statistical analyses will be conducted.

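### SAP 14 sets out to assess consistency of effect but reports no difference between subgroup effects, and its per-arm limit allows MMRM inference with a single subject in an arm (minor)

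*SAP*

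**What the plan says.** SAP 14 plans subgroup analyses of NPI-C apathy and NPI apathy in the mITT set "to assess consistency of the intervention effect across the following subgroups": age, sex, baseline NPI-C apathy (split at the median) and SSRI/SNRI use. The model is imported from Section 11: "Provided that the sample sizes in the subgroups allow, the MMRM analysis method described in" that section will be applied. The fits are separate: "The subgroup analysis will be performed by subgroup rather than including an interaction term". The fallback to descriptive statistics is worded "If the number of subjects within a subgroup is too small (less than 9 subgroup overall or less than 1 in any treatment group").

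SAP 11 defines the MMRM and its output: "the corresponding 80% and 95% CI of the differences and p-values will be provided". It has its own floor, counted in subjects with evaluable baseline and post-baseline data for the endpoint: if the number is "smaller than 15 (all treatment groups combined) or smaller than 2 in any treatment group, only descriptive statistical analyses will be conducted".

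SAP 13.2 (COMT status) also analyses by subgroup without an interaction term. It states no minimum size and does not name the model. SAP 15 does not mention the difference between the two floors. It does record that enrollment closed with the planned sample size not achieved. The final number of subjects is not stated.

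**The concern.** Consistency is a statement about the difference between two subgroup effects. Section 14 will show two effects, each with its own interval, but not their difference or its uncertainty. A reader who compares the two intervals by eye can see an inconsistency that is only noise.

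The floors add to this. A per-arm limit of fewer than 1 can be triggered only by an empty arm, so an LS mean resting on one person can carry a CI and a p-value. For a whole endpoint, the same SAP treats one subject in an arm, or 14 in total, as too few for that inference. With enrollment closed early, small subgroups are likely.

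At stake is how exploratory subgroup results are read when a later trial is planned. The primary safety objective is not touched.

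**Working it through.** **The plan's own figures.** SAP 4.1 gives 75 randomized 1:1:1, 20% discontinuation and the criterion "at a 2-sided alpha = 0.2 level (ie, an 80% confidence interval [CI] excluding zero"). With 25 × 0.8 = 20 completers per arm, noncentral-t power for 0.678 SD is 79.9%. With 20 × 0.8 = 16 per arm, power for 0.761 SD is 80.0%. Both stated figures reproduce and neither is disputed.

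**Width at each floor.** Assumptions: one visit (Week 12), complete data, covariates orthogonal to treatment. Residual df = n − 5 (intercept, baseline, two treatment terms, SSRI/SNRI use). Half-width = t(df) × sqrt(1/n1 + 1/n2), in residual SD units.

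| Floor | Split (active v placebo) | df | 80% | 95% |
|---|---|---|---|---|
| Section 14, n = 9 | 3 v 3 | 4 | 1.533 × 0.816 = 1.25 | 2.776 × 0.816 = 2.27 |
| Section 14, n = 9 | 4 v 1 | 4 | 1.533 × 1.118 = 1.71 | 2.776 × 1.118 = 3.10 |
| Section 14, n = 9 | 1 v 1 (7/1/1) | 4 | 1.533 × 1.414 = 2.17 | 2.776 × 1.414 = 3.93 |
| Section 11, n = 15 | 5 v 5 | 10 | 1.372 × 0.632 = 0.87 | 2.228 × 0.632 = 1.41 |
| Section 11, n = 15 | 2 v 2 (11/2/2) | 10 | 1.372 × 1.000 = 1.37 | 2.228 × 1.000 = 2.23 |

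Keeping 9 overall but requiring 2 per arm brings the worst case (5/2/2) to 1.533 × 1.000 = 1.53 SD at 80%. Within a level of SSRI/SNRI use that covariate is constant and drops out, so df rises by 1. The balanced 80% figures become 1.21 SD (n = 9) and 0.86 SD (n = 15).

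In NPI points, SAP 4.1 quotes a reference trial with "an effect size 0.5625 (mean difference of 1.8 and SD of 3.2"). If that SD applied here (an assumption), the balanced 80% half-widths would be 1.25 × 3.2 = 4.0 and 0.87 × 3.2 = 2.8 points, against a reference difference of 1.8. Because 3.2 is not a baseline-adjusted residual SD, these point figures tend to be too wide.

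**Misreading side-by-side intervals.** Assume an even split and the same true effect of 0.678 SD in both levels. Let p be the probability that one level's 80% CI excludes zero. The probability that exactly one of the two does is 2p(1 − p).

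| Evaluable | Per arm in each level | df | p | 2p(1 − p) |
|---|---|---|---|---|
| 60 (75 less 20%) | 10 | 25 | 0.586 | 0.485 |
| 48 (60 less 20%) | 8 | 19 | 0.522 | 0.499 |
| 30 (illustrative) | 5 | 10 | 0.410 | 0.484 |

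**What the missing difference would look like.** The two levels contain different subjects, so it is a subtraction: SE = sqrt(SE1² + SE2²) = sqrt(4/m) SD with m per arm in each level. In the balanced case the Satterthwaite df is the sum of the two df.

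- m = 10: 1.299 × 0.632 = 0.82 SD (80% half-width, df 50).
- m = 8: 1.304 × 0.707 = 0.92 SD (df 38).
- m = 5: 1.325 × 0.894 = 1.19 SD (df 20).

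**Number of contrasts.** 4 factors × 2 endpoints × 2 doses = 16. If effects are fully consistent, 16 × 0.2 = 3.2 of the 80% CIs are expected to exclude zero, whatever their correlation.

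**The case against.** Fitting by subgroup is an explicit, prespecified choice in a trial that the protocol calls a learning trial, with formal testing not the key objective (Protocol 9.1 and 9.4.2). A reader can approximate the difference from the estimates and intervals already planned. It would be imprecise, and 16 exploratory intervals would produce chance findings of their own. A smaller floor for subsets may be deliberate, and applying 15 to every level could remove most of the subgroup inference.

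Most of this stands, and it rules out several stronger readings that a reader might draw.

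- *Separate subgroup models are an error.* They are a stated choice and can stay.
- *The two overall minima contradict each other, so 15 must govern.* Section 11's limit qualifies the primary analysis of each PD endpoint, and Section 14 sets its own number for subsets. The lower number is unexplained, not contradictory.
- *The SAP will declare inconsistency about half the time.* The exclusion of zero is the detection criterion in SAP 4.1. Section 14 sets no such rule for subgroups. The 0.49 only illustrates how readers may misjudge paired intervals.
- *COMT inference has the same fault.* SAP 13.2 names no MMRM, CIs or p-values, so this applies only if that model is used there.

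The most unbalanced splits (7/1/1, 11/2/2) are limits of what the rules allow and are unlikely under 1:1:1 allocation.

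Two things remain. The aim as worded has no matching output, and the per-arm limit protects against nothing but an empty arm. Being exploratory does not settle either, because the plan still provides CIs and p-values.

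**Conclusion.** The point holds at minor severity. Section 14 plans no estimate of the quantity its aim names, and it allows MMRM inference with one subject in an arm where Section 11 would not. At the respective floors its 80% intervals are about 1.4 times as wide in the balanced case (1.25/0.87) and 1.6 times in the most unbalanced (2.17/1.37). These figures assume complete data and orthogonal covariates at a single visit. Actual subgroup counts are not in the documents, so how often the floor will bind is unknown.

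The counting units also differ: Section 11 counts subjects evaluable for the endpoint, Section 14 counts subjects in the subgroup. Since the SAP's mITT set already requires a post-baseline NPI-C apathy score, that gap matters mainly for NPI apathy and for missing baselines.

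The documents do not support extending the point to the primary safety analysis or to the overall PD comparisons.

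**What to change.** (a) In SAP 14, count subjects evaluable for the endpoint and require at least 2 per arm for within-subgroup MMRM CIs and p-values, as Section 11 does. Either adopt Section 11's overall minimum of 15 or state why 9 is enough for a subset. If MMRM is used for COMT in 13.2, state that the same floor applies.

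(b) Keep the by-subgroup models. Where both levels of a factor meet the floor, also report, for each endpoint and each dose versus placebo, the Week 12 difference between the two subgroup effects with its 80% CI. Take it as the difference of the LS-mean differences, with SE = sqrt(SE1² + SE2²) and Satterthwaite df. Label it exploratory and present it as an estimate, not a test.

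Cost: a few sentences in the SAP and up to 16 extra rows, with no new data or model. Downsides to state beside the table: about 3 of 16 such intervals would exclude zero by chance under full consistency, and the intervals are wide (80% half-width about 0.82 SD at 60 evaluable, 1.19 SD at 30). Some subgroups will become descriptive only. If the final N is small there may be no contrast at all: both levels need the minimum, so at least 2 × 15 = 30 evaluable, or 2 × 9 = 18 if 9 is kept.

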15. CHANGES IN THE PLANNED ANALYSIS

In addition to changes corresponding to protocol amendments, the analysis plan differs from the protocol analysis section as shown below

- Protocol specified 80% CIs will be presented. The SAP further specifies that both 80% and 95% CIs will be included ([Section 11](#)).
- The population of all subjects who consent to participate in the clinical trial was referred as “Enrolled” in the protocol but is labeled as “Screened” for further clarity in the SAP ([Section 4.3](#)).
- The mITT population is modified in the SAP ([Section 4.3](#)) as compared with the protocol to allow analysis evaluates dose effect in this exploratory study.
- Due to the early closure of enrollment with the planned sample size not achieved, the hypothetical strategy is the only approach taken for missing value handling. The protocol specified sensitivity analyses are no longer planned.

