On Day 22 (Visit 4), all subjects will take the Step 5 dose of IMP at the clinic. Subjects will be monitored for tolerability while undergoing concurrent assessments; after completion of all visit procedures, the investigator will assess whether the participant will continue with the new dose. Subjects who are unable to tolerate the dose at Step 5 may go back to the dose at Step 4 and continue on that dose for the remainder of the trial. Subjects who are able to tolerate the Step 5 dose will continue on this dose for the remainder of the trial and no further dosing adjustments are allowed.

[figure not shown]
Lack of tolerability should be of sufficient severity that it results in significant dysfunction or distress to the subject (eg, Common Terminology Criteria for Adverse Events [CTCAE] Grade 2/3). The medical monitor should be contacted in any instance

where the investigator is uncertain whether the subject is able to tolerate the stepwise dose increase.

No deviations in the dosing schedule, other than those noted above, are allowed.

The titration scheme, including the dosing decision time points, is presented in [Figure 2](#).

Figure 2 Dosing Schematic

Abbreviations: PBO = placebo.

Note: If “Yes” then continue with new dose; if “No” then stay at previous dose.

Assessments will be conducted at the Week 1, 3, 6, and 12 visits. Subjects will be instructed to take their dose of IMP at the clinic on days when visits occur. Blood samples for PK analysis will be collected at the Week 1, 3, 6, and 12 visits.

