9.4.2 Pharmacodynamic Analyses

Pharmacodynamic endpoints with repeated post-baseline assessments will be analyzed using a mixed-model repeated measures (MMRM) analysis, including baseline score (if applicable), treatment, concomitant SSRI/SNRI use, visit, and the interaction between treatment group and visit as fixed factors in the model. Subject will be included as a random effect in the model.

The trial is designed as a learning trial instead of a confirmatory trial. The key research question for the pharmacodynamic endpoints will be primarily addressed with an estimand based on the following attributes: 1) treatments as randomized regardless of the final dose level achieved following the titration steps, 2) subjects in the modified intent-to-treat (mITT) population who tolerate dose increases to at least Step 4 on Day 21 during titration as the target trial population, 3) change from Baseline to Week 12 as the key endpoint of interest, 4) the treatment differences estimated based on the least square mean and the corresponding 80% confidence interval from the MMRM model as the population level summary, and 5) a hypothetical strategy to address intercurrent events (ICEs) of potential death, treatment discontinuations, missed visits, and start of prohibited concomitant medications unless a treatment-related reason can be identified for a given ICE. If such reasons are identified, a composite strategy may be taken, eg, assigning highest severity to the case, to ensure appropriate interpretation of the data. Further details, including additional estimands for the research questions on the effect of combined CVL-871 treatment group versus placebo and on the effect of final dose levels of CVL-871 following the completion of titration versus placebo, will be described in the SAP.

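### SAP 15 drops the protocol's exception for treatment-related intercurrent events because enrolment closed early, so Week 12 values missing after a related stop are modelled as missing at random with no planned check

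*SAP*

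**What the plan says.** Protocol 9.4.2, repeated in the synopsis, defines the main pharmacodynamic estimand by five attributes. The fifth uses a hypothetical strategy for death, treatment discontinuation, missed visits and prohibited medication, "unless a treatment-related reason can be identified for a given ICE". For those cases it continues: "If such reasons are identified, a composite strategy may be taken, eg, assigning highest severity to the case".

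SAP 15 lists a departure from this. "Due to the early closure of enrollment with the planned sample size not achieved", it says, "the hypothetical strategy is the only approach taken for missing value handling". It adds: "The protocol specified sensitivity analyses are no longer planned". SAP 11 states the consequence: "the missing values will be considered as missing at random". SAP 17.3 plans no imputation.

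Two further rules decide who is affected. Protocol 4.1.2 lets a subject who cannot tolerate Step 5 return to Step 4, but once Step 5 is accepted "no further dosing adjustments are allowed". SAP 4.3 limits the mITT set to subjects who tolerated Step 4 and have a post-baseline NPI-C apathy score.

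**The concern.** The only reason given for removing the exception is the sample size. Assigning a score after a related stop needs no minimum number of subjects, and in a smaller trial each such stop carries more weight. The SAP also keeps methods that need more data than this. SAP 11 fits the MMRM with as few as 15 evaluable subjects overall, and SAP 14 allows it in subgroups of 9.

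The missingness could plausibly be drug-related. Nausea was the most frequent adverse event in both earlier trials (Protocol 2.2.4), and the titration exists to limit nausea and vomiting (Protocol 4.3). A subject who accepts Step 5 and later becomes intolerant has no dose adjustment available and can only continue or stop. Leaving the trial ends both treatment and participation (Protocol 7.2.3).

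If related stops fall mainly in the active arms, an analysis that relies only on missing at random will tend to look better for the drug than one that counts those stops as poor outcomes. The trial is meant to inform the dose range for later work (Protocol 4.3), so a difference linked to tolerability matters to its purpose.

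**Working it through.** **The plan's own figure.** Inputs from Protocol 9.2: 75 or 60 subjects, 1:1:1 allocation, 20% discontinuation, two-sided alpha 0.2, 80% power. Evaluable subjects per arm are 25 × 0.8 = 20 and 20 × 0.8 = 16. The normal approximation, (1.2816 + 0.8416) × √(2/n), gives detectable effects of 0.671 and 0.751. The noncentral t gives 0.678 and 0.761, which match the plan. The 20% is all-cause and enters only as lost numbers, so the documents give no rate for related stops.

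**Who can be affected.** NPI and NPI-C are scored after baseline only at Visit 5 (Day 43) and Visit 6/ET (Day 85). SAP 4.4.2 and 4.4.3 classify scores by the eCRF visit, and do not say how an early termination (ET) score is labelled.

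| Related intolerance or stop | ET visit attended | Consequence for Week 12 |
|---|---|---|
| Stop through Step 4 | either | Outside mITT; a separate selection question |
| Intolerance at Step 5, Day 22 | not applicable | Step-down allowed; need not be missing |
| Stop from Day 22 to Visit 5 | no | No post-baseline score; outside mITT |
| Stop from Day 22 to Visit 5 | yes | Observed if ET is labelled Visit 6; otherwise missing |
| Stop after Visit 5 | no | In mITT, missing, modelled as missing at random |
| Stop after Visit 5 | yes | Observed if ET is labelled Visit 6; otherwise missing |

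Only the last three rows can produce the problem, and two of them depend on the unstated slotting rule.

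**What is planned that might detect it.** SAP 13 covers adverse events by period and dose, and COMT status. SAP 14 covers subgroups. None of these varies the missing-data assumption.

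**Illustration only.** Take the protocol's reference difference of 1.8 NPI apathy points (SD 3.2) as an assumed MMRM result. Let a share q of one active arm, and none of placebo, have a Week 12 value missing after a related stop. Let P be the placebo mean change (negative means improvement) and W the change assigned to those subjects. The active mean change is (1 − q)(P − 1.8) + qW, so the difference in favour of the drug is

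D = 1.8(1 − q) + qP − qW.

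For zero change, W = 0. For highest severity, W = 12 − B, where B is the baseline score. The maximum is 4 × 3 = 12 (frequency times severity), and entry requires at least 2 × 2 = 4. The values of q, B and P are all assumed.

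| q | W = 0, P = 0 | W = 0, P = −2 | Highest severity, B = 8, P = 0 | Highest severity, B 4 to 12, P 0 to −2 |
|---|---|---|---|---|
| 5% | 1.71 | 1.61 | 1.51 | 1.21 to 1.71 |
| 10% | 1.62 | 1.42 | 1.22 | 0.62 to 1.62 |
| 20% | 1.44 | 1.04 | 0.64 | −0.56 to 1.44 |

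Example: q = 10%, B = 8, P = 0 gives 1.8 × 0.9 − 0.1 × 4 = 1.22. The 20% row is a high scenario, because 20% is the planned rate of all discontinuations, not of related stops that leave Week 12 missing within mITT.

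**Weight of one case.** In an assumed arm of 10, take one such subject with baseline 4. Assigning highest severity (+8) instead of zero change moves the arm mean by 8/10 = 0.8 points, or 0.8/3.2 = 0.25 SD.

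**The case against.** The strongest reply is that little was binding and few subjects are exposed. The composite strategy was something that might be used, with highest severity only as an example, so no composite estimate was ever fixed. SAP 15 lists the change openly, and SAP 1 says revisions were made before database lock. The MMRM does not simply give a subject the course of those who stayed: it uses that subject's own baseline and Week 6 scores. Pharmacodynamics is a secondary objective in a trial described as a learning trial. Discontinuations by reason (SAP 5.1), adverse events by relationship (SAP 9.1.1), adverse events leading to discontinuation by period (SAP 13.1) and individual NPI listings (SAP 11.1) would let a reader find the cases. A worst-score rule in a small arm is also volatile, as the last calculation shows.

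Most of this stands, and it limits the point. A reader might infer that the SAP broke a mandatory rule or concealed a change; the optional wording and the entry in SAP 15 do not support either reading. Two things survive. The clause withholding the plain hypothetical strategy from related events was part of the main estimand, even though its replacement was optional. The listings identify cases but do not show how far the estimate depends on them.

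**Conclusion.** The point holds as an unsupported rationale and a missing robustness check. Early closure does not justify treating related stops like any other missing value, and nothing planned shows what that choice does to the Week 12 estimates. SAP 15 also describes the change as missing-value handling and refers to withdrawn sensitivity analyses, although Protocol 9.4.2 names none under that label. What changed is the handling of treatment-related intercurrent events in the main estimand. Part of any gap between the two approaches is therefore a change in the question asked, not a failure of the model.

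The likely direction favours the drug, on the assumption that related stops are more frequent on active treatment. The size is unknown: the documents give neither the number of related stops nor the final sample size, and the slotting of ET scores is open. A reader might take the table as an estimate that the effect is overstated by a given fraction. It is not; every value of q, B and P in it is assumed.

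**What to change.** - Keep the MMRM as the primary analysis.
- For NPI-C apathy and NPI apathy at Week 12, add a supportive analysis with the same model terms. Values missing after a stop recorded as related to IMP are set (a) to the highest severity, which is the protocol's own example, and (b) to zero change from baseline, a milder case that the protocol does not name. For (a) the maxima are 12 for NPI apathy and 11 items × 3 = 33 for NPI-C apathy (SAP 17.4.1).
- Report both beside the MMRM with the number of such subjects by arm, and note that one case can move the result in a small arm.
- State whether ET scores count as Week 12.
- Reword SAP 15 to say that the handling of treatment-related intercurrent events in the main estimand has changed.

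The cost is four extra model fits (two endpoints by two rules) on data already collected. Causality is recorded for every adverse event (Protocol 10.3.3), and SAP 17.2.5 already counts a missing assessment as related. The drawback is a supportive estimate that may be less favourable and sensitive to single cases. If no related stops left Week 12 missing, the counts alone will show it.
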